7.2 MEDICAL HISTORY

Medical history will be coded using Medical Dictionary for Regulatory Activities (MedDRA). Medical history of interest including Chronic Kidney Disease (CKD) history inclusive of CKD cause, cardiovascular disease, cerebrovascular disease, thrombosis history, hypertension history, diabetes history, and anemia history will be summarized by system organ class and preferred term for the safety population.

8 TREATMENT AND MEDICATIONS

8.1 STUDY DRUG EXPOSURE

Exposure to study medication will be summarized in terms of treatment duration in weeks, which is calculated using the following formula: (the date of last medication taken - the date of first dose taken +1)/7.

Total weekly study drug exposure is defined as the total actual dose (in mg and mg/kg) of study drug administered within the week (windowed by 7-day period from Day 1).

Weekly exposure and total study drug exposure will be tabulated for the safety population.

Per administration amount and administration frequency will also be tabulated for the safety population.

Patient-Exposure-Year (PEY) is defined as (Last Dose Date – First Dose Date + 1)/365.25.

8.1.1 Dosing Changes

Prescribed dose adjustments (dose increase, dose reduced, dose interrupted, and dose resumed) along with the adjustment reasons (protocol mandated dose amount adjustment, AE related, and other) recorded on the Prescribed Dose Adjustments Form in the eCRF will be tabulated by time point (Week 2, 4, 6, 8, 12, 16, 20, 24). Mean number of dose adjustments (including dose-hold) during study and number (%) of subjects with dose adjustment in each adjustment category will be summarized.

8.1.2 Treatment Compliance

Study medication dosing compliance for a specified period is defined as the total dose (mg actually taken by a patient during that period divided by the prescribed dose expected to be taken during the same period multiplied by 100. An overall per-dose compliance measure can be calculated by (total amount of actual dose administrations)/ (total amount of expected dose administrations) *100 during the subject's treatment period. Descriptive statistics for study medication compliance will be presented for the entire treatment period of the study.

Compliance will be summarized as follows:

- Descriptive statistics will be summarized for the entire treatment period.
- Percent compliance will be categorized according to the following categories for the entire treatment period for safety population:
 - less than 75% (drug noncompliance)
 - at least 75%, less than 125% (drug compliance)
 - greater or equal 125% (drug noncompliance)
 - unknown

8.2 PRIOR AND CONCOMITANT MEDICATIONS

The World Health Organization Drug Dictionary (WHO Drug) will be used to classify prior and concomitant medications by therapeutic class and generic name based on ATC code level 3. Prior medication is defined as any medication taken and stopped prior to the first dose of the study medication. Concomitant medication is defined as any medication taken between the day of first dose of the study medication and the day of last study medication date + 28 days. For subjects who complete the treatment period and decide to participate in the extension treatment, any medication taken after the Treatment Period (Week 24/EOT) will not be counted as concomitant medications for the main study, but will be listed for the extension period.

Medication start and end dates and times will be compared with the start date of study drug and classified as per [Table 4](#).

In case of partial or missing dates, comparisons will be made based on the level of detail available. For example, if start date of study drug is 04Jan2013, and a medication has a start date of Jan2013 but missing day, the medication will be classified as concomitant.

Table 4. Classification of Prior and Concomitant Medications

Start date \ End date	Before start of study drug administration	On or after start of study drug administration	Missing
Before start of study drug administration	Prior	Concomitant	Concomitant
On or after start of study drug administration	—	Treatment Emergent Concomitant	Treatment Emergent Concomitant
Missing	Prior	Concomitant	Concomitant

Both prior and concomitant medication usage will be summarized by the number and proportion of subjects. Subjects will only be counted one time in each unique ATC Class and generic name if multiple drugs are used by a subject.

Detailed analyses may be performed on prior and concomitant medications of special interests such as oral iron, blood pressure medications, and lipids medications.

9 EFFICACY ANALYSES

Efficacy analysis will be conducted on the FAS population.

9.1 ANALYSIS OF EFFICACY ENDPOINTS

9.1.1 Proportion of subjects with mean Hb ≥ 10 g/dL, averaged from Week 16 to Week 24

The efficacy endpoint will be evaluated using the proportion (%) of subjects with mean value of Hb measurements from Week 16 to Week 24 ≥ 10 g/dL.

Proportion of responders will be presented descriptively with counts and percentages and a 95% confidence interval of the responder rate. The 95% CI of the response rate will be presented based on normal approximation.

For the Hb efficacy analysis, a multiple imputation (MI) method will be used. This will be implemented on the raw Hb values, then the Hb-relates endpoint summaries will be derived based on the imputed data (algorithm as used for the previous phase 3 studies).

The following steps will be used to conduct the MI procedure of the Hb values:

1. Generate 200 datasets, using seed 12345, where only intermittent missing Hb data will be imputed relying on non-missing data from all subjects using the Monte Carlo Markov Chain (MCMC) imputation model using baseline Hb and the available non missing Hb for each scheduled week.

The MCMC statement in the SAS PROC MI procedure with monotone option will be used. As a result, each dataset will only have missing ending data, or a monotone missing data pattern.

2. For each dataset from step 1, missing ending data (Hb up through end of evaluation period) will be imputed. As a result, 200 imputed complete datasets will be generated.

- Missing data at Week 2 will be imputed using the regression imputation model with baseline and Hb from Week 2, using the SAS PROC MI procedure with the REGRESSION option in the MONOTONE statement.
- Repeat for all other scheduled weeks sequentially (Week 4 to the end of evaluation period). Subjects whose missing data were imputed for previous weeks will contribute to the imputation for the current week.
- The regression imputation model includes an intercept and the slopes of the Hb from previous weeks.

Steps 3 and 4 will be used to analyze proportion of subjects with a mean Hb level ≥ 10 g/dL, averaged from Week 16 to Week 24 using the imputed Hb data above:

3. Analyze each imputed complete dataset to estimate proportions of responders and their standard errors using the mean of all observed or imputed Hb values within the evaluation period (Weeks 16 to 24).

Sample SAS code:

```
PROC FREQ DATA=xx;
  TABLES resp_week16_24 / cl binomial (level=2);
  BY _Imputation_;
  ODS OUTPUT BINOMIALPROP=prop;
RUN;
```

4. Combine estimates from the results for each of the 200 proportion estimates using SAS PROC MIANALYZE.

```
PROC MIANALYZE DATA=prop;
  MODELEFFECTS prop;
  STDERR prop_se;
  ODS OUTPUT PARAMETERESTIMATES=mian_prop;
RUN;
```

Report the results of the proportion of subjects with a mean Hb level ≥ 10 g/dL, averaged from Week 16 to Week 24.

9.1.2 Mean Hb change from baseline to average Hb from Week 16 to Week 24

For continuous endpoints, changes from baseline will be presented descriptively. Missing Hb values will be imputed using a MI procedure.

Steps 3 and 4 below will be used to calculate the mean Hb change from baseline to average Hb from Week 16 to Week 24 using the imputed Hb data in Steps 1-2 above in [section 9.1.1](#).

3. Analyze each imputed complete dataset to estimate the mean Hb change from baseline to average Hb and their standard errors using the mean of all observed or imputed Hb values within the evaluation period (Weeks 16 to 24).

Sample SAS code:

```
PROC MEANS DATA=xx MEAN STDERR;  
  BY _imputation_;  
  VAR change_Week24;  
  WEIGHT covariates;  
  OUTPUT OUT=avg MEAN=mean_hb STDERR=se_hb;  
RUN;
```

4. Combine estimates from the results for each of the 200 proportion estimates using SAS PROC MIANALYZE.

```
PROC MIANALYZE DATA= avg;  
  MODELEFFECTS mean_hb;  
  STDERR se_hb;  
  ODS OUTPUT PARAMETERESTIMATES=mian_mean;  
RUN;
```

Report the results of the mean Hb change from baseline to average Hb from Week 16 to Week 24.

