3. OBJECTIVES AND ENDPOINTS

3.1. Objectives

3.1.1. Primary Objectives

To confirm safe and effective Roxadustat dosing regimens among in-center HD subjects converted from ESA therapy (>=6 weeks ESA treatment) or who are ESA-naïve (<6 weeks ESA treatment).

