5. STUDY ENROLLMENT AND WITHDRAWAL

5.1. Inclusion Criteria

A subject is eligible for the study if all of the following criteria are met:

- 1. Subject has been informed of the investigational nature of this study and has given written informed consent in accordance with institutional, local, and national guidelines
- 2. Subject is ≥ 18 years of age
- 3. Receiving in-center hemodialysis for end stage renal disease (ESRD)
- 4. Prior ESA use:
 - For a subject converting from an ESA: On ESA ≥6 weeks and the prescribed ESA dose remain stable (as determined by PI) during the 4 weeks prior to initiating roxadustat treatment
 - Subject is initiating anemia treatment: Defined as: < 6 weeks of prior ESA use or no prior ESA use.
- 5. Vascular access must be a functioning native arteriovenous fistula or graft with adequate flow in the opinion of the investigator, or permanent tunneled catheter.
- 6. Screening Hb (based on central lab value; measured within 10 days prior to initiating roxadustat treatment):
 - Subjects converting from an ESA: screening Hb is between 9.0 to 12.0 g/dL
 - Subjects initiating anemia treatment: screening Hb is < 10.0 g/dL
- 7. Ferritin ≥ 50 ng/mL, Transferrin saturation (TSAT) ≥ 10% at screening (subject may qualify after receiving iron supplement per local standard of care)
- 8. Subject's alanine aminotransferase (ALT) and aspartate aminotransferase (AST) are ≤ 3 x upper limit of normal (ULN), and total bilirubin (TBL) is ≤ 1.5 x ULN at screening and prior to initiating roxadustat treatment. TBL up to 2 x ULN may be allowed if AST and ALT are within normal limit)
- 9. Subject's body weight (estimated dry weight in HD subjects) is 45.0 to 160.0 kg

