2 STUDY DESIGN

[figure not shown]
This open-label single arm study is designed to evaluate roxadustat in maintaining hemoglobin (Hb) in ESRD subjects receiving in-center hemodialysis either after conversion from a stable ESA dose: ESA use \geq 6 weeks prior to conversion to roxadustat dosing or as initial anemia treatment, in subjects with < 6 weeks of total ESA use prior to start of roxadustat dosing.

The study periods are as follows:

- **Screening Period:** Up to 6 weeks
- **Treatment Period:** 24 weeks
- **Post-Treatment Follow-Up Period:** Subjects permanently discontinuing roxadustat, should have one final safety assessment (Treatment Emergent Adverse Events (TEAEs) and Treatment Emergent Serious Adverse Events (TESAEs)) 28 days after the last roxadustat dose.

An extension of roxadustat treatment after 24 weeks may be offered to interested subjects within the context of the study protocol upon agreement with the study site. Data listings for the extension phase will be generated upon database lock and will include serious adverse events (SAEs), concomitant medications related to SAEs, and hospitalization records related to SAEs.

Study Design Overview

Primary Efficacy Endpoint: • Proportion of subjects with mean Hb \geq 10.0 g/dL, averaged over weeks 16-24

Secondary Efficacy Endpoints: • Proportion of subjects with mean Hb between 10-12 g/dL, averaged from week 16 through week 24

Conversion subjects:

- Mean Hb change from baseline to average Hb from week 16-24

Subjects will be dosed three times weekly (TIW), except if a subject requires < 60 mg/week to maintain Hb levels, in which case dose frequency may be reduced in a stepwise fashion, e.g., to twice weekly (BIW), then once weekly (QW).

Initial Dose

Conversion from ESA to Roxadustat

The initial roxadustat dose is determined using a conversion table based on the subject's previous prescribed ESA dose in the last 4 weeks prior to enrollment (for Mircera®:in the last 8 weeks prior to enrollment) (Table 1.1).

Roxadustat treatment should start after the following intervals:

- Two days after stopping epoetin
- One week after stopping darbepoetin alfa
- Two weeks after stopping methoxy polyethylene glycol-epoetin beta (Mircera®)

If the converted initial dose exceeds the maximum dose of 3.0 mg/kg/dose then the next-lower dose step should be chosen as the initial dose.

Table 1.1. Conversion from ESA to Roxadustat

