3 STUDY OBJECTIVES

3.1 PRIMARY OBJECTIVE

To confirm safe and effective roxadustat dosing regimens among chronic dialysis subjects converted from ESA therapy (≥ 6 weeks ESA treatment) or who are ESA-naïve (< 6 weeks ESA treatment).

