4.2 EXPLORATORY ENDPOINTS

- Proportion of subjects with a mean Hb level within 10-12 g/dL from Week 16 to Week 24
- Proportion of subjects with Hb > 12 g/dL any time during treatment
- Proportion of subjects with Hb > 13 g/dL any time during treatment
- Percentage of time with Hb, values within 10.0 to 12.0 g/dL from Week 16 to Week 24
- Time to first RBC transfusion
- Proportion of subjects with a mean Hb level ≥ 10 g/dL in the first 8 weeks after conversion or initiation of treatment
- Proportion of subjects with a mean Hb level ≥ 10 g/dL (averaged from Week 16 to Week 24) based on baseline ESA use status ≥ 6 weeks (conversion from ESA to roxadustat based on prior ESA use) and < 6 weeks (initiation of roxadustat based on body weight)
- Evaluate the utilization of IV iron (IV iron use/4 weeks)

- Evaluate the effect on iron indices
- Evaluate dosing adherence
- Conversion subjects: Comparison of starting dose of roxadustat to roxadustat dose at Weeks 16 to 24
- Mean number of dose adjustments (including dose-hold) during study
- Proportion of subjects requiring blood/pRBC transfusion from Week 5 (Day 29) to Week 24/ET.
- Proportion of subjects requiring rescue therapy (blood/pRBC transfusion or ESA rescue) from Week 5 (Day 29) to Week 24/ET

In addition to the exploratory endpoints in the protocol, additional exploratory efficacy endpoints of interest are presented in this section.

RBC transfusion data is collected in the Blood Transfusions form of the eCRF.

For efficacy evaluation, Hb values will be censored for 4 weeks if blood/pRBC is administered during the treatment period. Hb results obtained from the central laboratory will be used to determine the Hb response.

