9.3 SUBGROUP ANALYSIS

Primary efficacy endpoints will be presented by forest plots based on the following subgroups: sex, age group, baseline Hb categories, baseline iron status, cardiovascular/cerebrovascular/thromboembolic medical history, starting dose, participating dialysis organizations, and baseline ESA dose categories. Overall summary of TEAEs will be analyzed by subgroups of starting doses of roxadustat.

Other endpoints of interest may be analyzed by the subgroups listed above as needed.

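### SAP 9.1.2 reports mean Hb change as one value pooled over conversion and initiation subjects, which conflicts with SAP 2, and no mean-change or TEAE summary by ESA-use status is specified

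*SAP*

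**What the plan says.** Protocol 3.1.1 and SAP 3.1 name two populations in the primary objective. The protocol's aim is "To confirm safe and effective Roxadustat dosing regimens among in-center HD subjects converted from ESA therapy" or in subjects with less than 6 weeks of ESA use. The two groups have different starting-dose rules (prior ESA dose or body weight) and different entry criteria. In Protocol 5.1, for conversion, "screening Hb is between 9.0 to 12.0 g/dL"; for initiation, "screening Hb is < 10.0 g/dL". Both are then titrated to 11 g/dL by the same algorithm.

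SAP 4.1 defines the second efficacy endpoint, Hb change to the Weeks 16–24 average, without restricting it to a cohort. SAP 9 places all efficacy analysis on the FAS. The instruction in SAP 9.1.2 is to "Analyze each imputed complete dataset to estimate the mean Hb change from baseline to average Hb and their standard errors". Its sample code groups by imputation number only. The overview in SAP 2 has the same endpoint, "Mean Hb change from baseline to average Hb from week 16-24", under a label for conversion subjects.

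SAP 4.2 and 9.2.2 do plan the Weeks 16–24 responder proportion by ESA-use status. They also define an early responder proportion, "in the first 8 weeks after conversion or initiation of treatment", whereas Protocol 3.2.2 refers only to the period after conversion. On safety, SAP 9.3 states: "Overall summary of TEAEs will be analyzed by subgroups of starting doses of roxadustat". ESA-use status is not in the SAP 9.3 subgroup list.

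**The concern.** One group enters with Hb to be maintained and the other with Hb to be corrected. A mean change taken over both is a weighted average of two different quantities, and the weights are whatever enrolment delivers. The synopsis states that stratification does not apply, and neither document gives a target number per cohort.

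An expected rise in initiation subjects could therefore offset a modest fall after conversion. Such a fall is something the conversion regimen needs to be checked for. The pooled figure would also be hard to compare with any other study that had a different mix. Since the SAP gives two readings of who is in this endpoint, the choice should be fixed before results are seen.

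The objective also covers safety in both populations, yet no adverse-event table by ESA-use status is specified.

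**Working it through.** **Inputs from the documents.** Entry Hb 9.0–12.0 and below 10.0 g/dL (Protocol 5.1); common target 11 g/dL (SAP 2); N = 300 and assumed responder rate 80% (SAP 5.2). **Assumed, because the documents give none:** initiation share w, mean baselines, mean changes and SDs.

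**1. The plan's own figure.** The only precision figure concerns the pooled responder proportion: width 9.5%. The exact interval for 240/300 is 75.02% to 84.38%, width 9.36 points, close to the stated value. No precision is stated for the mean change, so there is nothing to reproduce there.

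**2. Formula.** Pooled change = (1 − w) × Δconv + w × Δinit. It is zero at w = −Δconv / (Δinit − Δconv).

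**3. Both cohorts reach 11 g/dL.** Pooled change in g/dL:

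| Baseline conv / init | Δconv / Δinit | w = 5% | 10% | 20% | 30% | 50% |
|---|---|---|---|---|---|---|
| 10.5 / 9.0 | +0.5 / +2.0 | 0.575 | 0.65 | 0.80 | 0.95 | 1.25 |
| 11.0 / 8.5 | 0 / +2.5 | 0.125 | 0.25 | 0.50 | 0.75 | 1.25 |
| 10.0 / 9.5 | +1.0 / +1.5 | 1.025 | 1.05 | 1.10 | 1.15 | 1.25 |

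The dependence on mix is large in the second row and small in the third.

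**4. Conversion subjects fall.** Pooled change in g/dL:

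| Δconv / Δinit | w = 10% | 20% | 30% | zero at w |
|---|---|---|---|---|
| −0.3 / +1.5 | −0.12 | +0.06 | +0.24 | 0.3/1.8 = 16.7% |
| −0.25 / +1.5 | −0.075 | +0.10 | +0.275 | 0.25/1.75 = 14.3% |
| −0.5 / +1.5 | −0.30 | −0.10 | +0.10 | 0.5/2.0 = 25% |
| −0.5 / +2.0 | −0.25 | 0.00 | +0.25 | 0.5/2.5 = 20% |

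In the first row, w = 40% gives 0.6 × (−0.3) + 0.4 × 1.5 = +0.42. From an assumed conversion baseline of 10.5, a fall of 0.3 leaves the cohort mean at 10.2, still above the responder threshold.

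**5. Do the subgroups in SAP 9.3 stand in for ESA-use status?**

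- Baseline Hb below 10: mixes initiation subjects with conversion subjects at 9.0–9.9.
- Baseline ESA dose: the low category in SAP Table 3 starts at 0, so it does not separate untreated initiators from low-dose converters.
- Starting dose: 70 and 100 mg occur in both cohorts; 150 mg appears in the dosing tables only for conversion.
- Coverage: the forest plots are for primary efficacy endpoints, and SAP 2 labels only the responder proportion as primary. Whether mean change is included is unclear, and subgroup analysis of other endpoints is discretionary.

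**6. Precision after splitting.** The 95% half-width is 1.96 × SD/√n. With SD 1.0 to 1.5 g/dL: n = 30, 0.36–0.54; n = 60, 0.25–0.38; n = 240, 0.13–0.19; n = 270, 0.12–0.18. For an 80% proportion the exact interval widths are 30.9 and 9.9 points at 30/270, and 21.5 and 10.5 points at 60/240.

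**The case against.** The strongest reply is that the lead endpoint already answers the cohort question. The Weeks 16–24 proportion at or above 10 g/dL comes first in SAP 4.1, is the basis for the sample size, and is planned by ESA-use status with multiple imputation. A fall that took many converters below 10 would show there. SAP 7.1 also plans baseline characteristics, iron indices and IV iron by cohort, and the starting-dose comparison is defined for conversion subjects. This stands. A reader might infer that the plan cannot confirm either regimen, and the documents do not support that. What stays exposed is a fall that leaves most converters at or above 10.

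The baseline Hb ≥ 10 stratum should consist mostly of converters, since initiators must screen below 10.0. That would help if the forest plots cover mean change, which is uncertain.

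A reader might also infer that the cohorts are expected to move in opposite directions. They are not: they share a target of 11, and the conversion entry range has midpoint 10.5, so the contrast is level or slightly up against rising. Nor is safety wholly pooled, because the 150 mg group isolates some conversion subjects.

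Two cautions apply. SAP 1 puts table specifications in a separate document, which may contain cohort columns. And the label in SAP 2 sits in overview text, so it is weak evidence of intent. It still conflicts with SAP 4.1 and 9.1.2. The study is descriptive, without hypothesis tests, so the gain is in interpretation and not in error control.

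**Conclusion.** The point holds in a limited form. As written, SAP 9.1.2 gives one mean Hb change over two cohorts with different entry Hb and different aims. The value depends on an enrolment mix that the documents do not set, and it could hide a modest post-conversion fall that stays above 10 g/dL. SAP 2 contradicts SAP 4.1 and 9.1.2 on whom the endpoint covers. No mean-change or TEAE summary by ESA-use status is specified.

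The size is not a property of the plan. Over initiation shares of 5% to 50%, the pooled change moves by about 0.2 g/dL or by more than 1 g/dL depending on assumed baselines. The share at which a fall is cancelled ranges from 14% to 25% across the pairs tried. A reader might take the 17% crossing as a finding about this trial; it follows only from the assumed −0.3 and +1.5 g/dL.

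This is a cheap improvement. It does not invalidate the efficacy plan.

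**What to change.** - **SAP 9.1.2:** report mean Hb change separately for conversion and initiation subjects, with the pooled value as supportive.
- **SAP 2, 4.1 and 9.1.2:** reconcile the endpoint's population so that all three agree.
- **SAP 9.2.2:** report the first-8-weeks proportion at or above 10 g/dL by cohort, since Protocol 3.2.2 defines it after conversion and initiation subjects start below 10 by design.
- **SAP 9.3 and 10.1.1:** add ESA-use status (≥ 6 versus < 6 weeks) to the subgroup list and to the overall TEAE summary.

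The cost is SAP wording and some extra table columns. ESA-use status is already defined in SAP 7.1 and used in 9.2.2, so no new data are needed. The downside is wider intervals in the smaller cohort: with 60 initiators and an SD of 1.0 to 1.5 g/dL, about ±0.25 to ±0.38 g/dL for the mean change. That is the precision the trial would have for that regimen under those assumptions.
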